6.1.4 Safety Population

The Safety Population will include all subjects in the ITT Population who receive a complete or partial dose of BE1116 or placebo, based on the treatment actually received.

7 General Considerations

Datasets will be created according to Clinical Data Interchange Standards Consortium (CDISC) standards. Study data will be provided in Study Data Tabulation Model (SDTM) format. Analysis data will be provided in Analysis Data Model (ADaM) format.

SAS version 9.4 or higher will be used to perform all data analyses.

Summaries of continuous variables will be in terms of the number of observations, mean, standard deviation, median, first quartile (Q1), third quartile (Q3), minimum and maximum.

Categorical variables will be summarized using frequency counts and percentages.

Analyses that use other descriptive statistics will have the specific descriptive statistics identified with the analysis in the applicable SAP section.

For all Bayesian analysis, posterior credible intervals will be reported, based on the quantiles of Markov Chain Monte Carlo (MCMC) samples. Point estimates will be based on posterior means.

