10.1.2 Primary Efficacy Analysis

A Bayesian logistic regression will be used to compare all-cause 6-hour mortality rate between the BE1116 and placebo arms, in the mITT Population.

Hypotheses:

Null Hypothesis (H_0): The all-cause 6-hour mortality rates in BE1116 is no better than control.

$$p_{kcentra} - p_{control} \geq 0$$

Alternative Hypothesis (H_1): The all-cause 6-hour mortality rate in BE1116 is lower than control.

$$p_{kcentra} - p_{control} < 0$$

Let y_i be the outcome of all-cause 6-hour death (1 = yes, 0 = no), the model is:

$$y_i \sim Bernoulli(p_i)$$

$$\text{logit}(p_i) = \beta_0 + \beta_1 \text{treatment}_i$$

where p_i is the probability of all-cause 6-hour mortality for subject i and $treatment_i$ is an indicator variable for treatment with BE1116. The coefficient β_0 is the effect of placebo on the primary outcome in the logit scale. The coefficient β_1 is the treatment effect of BE1116 over placebo on the primary outcome in the log-odds ratio scale.

While this model gives direct estimates of ORs, the absolute risk differences (primary outcome of interest) will be derived using posterior draws from the coefficients. We assume independent normal prior distributions for the regression coefficients of the form:

$$\beta_0 \sim Normal(\mu_0, \tau_0^2)$$

$$\beta_1 \sim Normal(\mu_1, \tau_1^2)$$

where, μ s and τ s are respectively the means and standard deviations of distributions.

The following priors are used:

$$\beta_0 \sim Normal(0, 10^2)$$

$$\beta_1 \sim Normal(0, 1^2)$$

These priors are centered at zero, which for β_1 corresponds to a priori no intervention effect. The prior for β_0 is noninformative, while the prior for β_1 is only very weakly informative and allows for considerable uncertainty; the 95% interval for β_1 on the OR scale ranges from 0.14 to 7.1.

The study will be considered a success and primary objective considered met if the posterior probability

$$\text{Prob}(p_{kcentra} - p_{control} < 0 | \text{data}),$$

of lower all-cause 6-hour mortality in the BE1116 arm compared with the placebo arm is greater than the success threshold.

For the final analysis the planned success threshold for the posterior probability will be 97.5%.

The Bayesian logistic regression model will be fitted via Markov Chain Monte Carlo (MCMC) methods in SAS (Version ≥ 9.4) using the PROC MCMC procedure. For each analysis, 4 MCMC chains will be run with a minimum burn-in of 3000 iterations and

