10.1.4 Subgroup Analyses of Primary Endpoint

Subgroup analyses will be used to help determine whether the treatment effect for the primary endpoint is homogeneous across the study population.

Subgroups of interest for this study are as follows:

- Mechanism of trauma injury: penetrating, or blunt .
- Presence of Head Injury: as indicated by Abbreviated Injury Scale(AIS) score > 0 in the “head” region).
- Sex: male, or female.
- Race: White, Black or African American, or Other.
- Age (< 18 years, 18 to 25 years, 26 to 64 years, or > 64 years).

- Weight-based dosing (2000 IU, or 3000 IU).
- IP administration start of infusion (Up to 45 minutes after hospital arrival, or > 45 minute to 90 minutes after hospital arrival.)
- Mode of transport: helicopter, ambulance, or self-presenting.
- RABT: $RABT \leq 2$, or $RABT > 2$.
- Blood pressure at admission: < 70 Systolic, or ≥ 70 Systolic mmHg.
- Glasgow Coma Scale at admission: by categories ≤ 8 , 9 to 12, 13-14.
- Injury Severity Score using the following categories:
 - Mild (1-8)
 - Moderate (9-15)
 - Severe (16-24)
 - Profound (≥ 25)
- Whether Fibrinogen was administered before study treatment: yes/no.
- Whether Cryoprecipitate was administered before study treatment: yes/no.
- Whether Tranexamic Acid was administered before study treatment: yes/no.

For the subgroup analysis the primary analysis model will be calculated within each level of the subgroup variable. For mechanism of trauma injury, a subject can have both blunt and penetrating injuries. In this case, the subject is included in both subgroups.

Credible intervals for the mortality within each treatment arm and the posterior probability for a lower mortality in the active treatment arm will be presented for each level of the subgroup variables.

Subgroup analysis of penetrating versus blunt trauma injury will provide evidence of BE1116 efficacy and safety in these populations with different mechanisms of traumatic injury. Blunt trauma, also called nonpenetrating trauma or blunt force trauma, is an injury to the body caused by forceful impact, injury, or physical attack with a dull object or surface. It is in contrast to penetrating trauma, in which an object pierces the body surface, causing an open wound ([NIGMC, 2018](#)).

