10.2.6 Subgroup Analyses of Secondary Endpoints

The same subgroup analyses as for the primary endpoint will be conducted for secondary efficacy endpoints using the analyses described in [Section 10.1.4](#).

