For the simulation instead of calculating the model for each of the 1000 datasets generated at an interim for futility analysis the results are looked up in the library (using a proc sql left join). A check was added to detect any potential cases where a simulated dataset is not covered by the library due to having more than 1024 events in either treatment arm.

Since 1024 events is more than 25% of the final treatment arm size of 4000 it was not considered likely for this event to happen given the sample size and assumed true event rates of 10%.

When running the simulation, the check was not triggered.

Technical Details

Due to the long initial time needed for computation the program has the following additional properties:

- After every 250 simulations the results are saved. In case of interruptions, the program will resume at the last completed multiple of 250.

- The simulation program is written so it can be executed multiple times in parallel for faster execution. A macro variable serves as an identifier about which instance this is. However, this was not used to generate the results described in this SAP.
- Per study design there is no stop for efficacy at the first analysis. This was implemented by setting an impossible (>1) threshold for the posterior probability at the first interim analysis instead of writing custom code for the first analysis. As the interim analysis models are used to generate the datasets for futility analysis, it is still necessary to calculate the model at the first stage.
- Since whether the study is stopped or not is based only on the results for the primary endpoint, the success thresholds for the secondary analysis can be changed in the program summarizing the operating characteristics without rerunning the simulation.

Reproducibility

Reproducibility is achieved as follows: whenever a batch of 250 simulations is started the seed is set to 100000 times the instance identifier (always set to 1 here) + the number of simulations already completed. The state of the random generator is then carried forward by using %sysranend.

As the range of allowable seeds is smaller for the proc surveyselect and proc mcmc procedures used than for data steps, those procedures are seeded with a seed generated in a data step that is in the appropriate range, e.g. using code like this:

```
data _NULL_;  
call streaminit(&sysranend);  
seedssurvey = %RandBetween(1, 2147483647);  
call symput('seedssurvey', seedssurvey);  
run;
```

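### In a subgroup level with no deaths in either arm, the planned Normal(0, 10²) prior on β0 makes the arm-level mortality intervals much too narrow (minor; subgroup display only)

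*SAP*

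**What the plan says.** SAP 10.1.2 models 6-hour death by logistic regression on treatment, with β0 ~ Normal(0, 10²) for the placebo logit and β1 ~ Normal(0, 1²) for the log odds ratio. It says that the β0 prior "is noninformative, while the prior for" β1 is only very weakly informative.

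SAP 10.1.4 carries this model into the subgroups: "For the subgroup analysis the primary analysis model will be calculated within each level of the subgroup variable". The listed output is: "Credible intervals for the mortality within each treatment arm and the posterior probability for a lower mortality in the active treatment arm will be presented". SAP Section 7 adds that "posterior credible intervals will be reported, based on the quantiles of Markov Chain Monte Carlo (MCMC) samples", with posterior means as point estimates. The 95% level is read across from SAP 10.1.2; SAP 10.1.4 does not restate it.

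SAP 10.2.6 extends the scheme: "The same subgroup analyses as for the primary endpoint will be conducted for secondary efficacy endpoints".

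These sections set no minimum number of subjects or deaths per level, no alternative prior, no pooling across levels and no check of sensitivity to the prior.

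**The concern.** A normal prior with SD 10 on the logit scale is flat only on that scale. As a statement about a proportion it is U-shaped, with most of its mass next to 0% and 100%. In the whole mITT Population there are enough deaths for this not to matter. In a level with no deaths in either arm, nothing in the data holds the intercept up. The posterior slides towards zero and takes the upper limit with it.

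Such levels are plausible. The study stopped before the first interim analysis, planned at 2000 subjects. The mITT Population was narrowed further, to subjects with GCS below 15 (or missing or not testable) and a transfusion before randomization. SAP 10.1.4 lists 15 subgroup variables, with levels such as age under 18, ISS 1-8, self-presenting, and fibrinogen given before study treatment. A handful of patients without a death would then be shown with an interval that looks like firm evidence of near-zero mortality. That is a poor basis for the stated purpose of judging whether the effect is homogeneous.

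**Working it through.** **Inputs from the SAP.** The two priors and the model (10.1.2); refitting by level and the listed outputs (10.1.4); quantile-based intervals (Section 7); a planning mortality of 10%, with 8% and 12% also simulated (16.2). **Assumed, because the documents give no figure:** 5 to 50 subjects per arm in a level, equal true mortality in both arms, and a mortality of 5% as a lower-risk case.

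**The plan's own figures first.** The prior interval for the odds ratio is exp(±1.96 × 1) = 0.141 to 7.10, which matches the SAP statement that β1 "on the OR scale ranges from 0.14 to 7.1". A re-simulation of the original design (10% placebo mortality, 20% relative reduction) gave 83.2% overall success against 82.9% in SAP Table 4. Under no effect it gave 1.81% against 1.94%. The model is therefore being read as the SAP intends.

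**Shape of the β0 prior.** Prior mass below 1% or above 99% = 2 × [1 − Φ(ln(99)/10)] = 2 × [1 − Φ(0.4595)] = 0.646. Prior mass below 0.1% or above 99.9% = 2 × [1 − Φ(ln(999)/10)] = 2 × [1 − Φ(0.6907)] = 0.490.

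**Upper limit with no deaths in either arm.** The joint posterior of β0 and β1 was integrated on a grid and the 97.5% quantile of placebo mortality was read off. With no events in n subjects the exact limit is 1 − 0.025^(1/n). Pooling both arms replaces n by 2n.

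| Deaths | SAP model | Exact, one arm | Exact, both arms pooled |
|---|---|---|---|
| 0/10 v 0/10 | 4.8 to 4.9% | 1 − 0.025^(1/10) = 30.8% | 1 − 0.025^(1/20) = 16.8% |
| 0/20 v 0/20 | 2.5% | 1 − 0.025^(1/20) = 16.8% | 1 − 0.025^(1/40) = 8.8% |
| 0/50 v 0/50 | about 1.0% | 1 − 0.025^(1/50) = 7.1% | 1 − 0.025^(1/100) = 3.6% |

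The first entry depends slightly on the grid step: 4.8% on a coarse grid and 4.9% on a fine one. Jeffreys single-arm limits are 21.7% at 0/10 and 11.7% at 0/20. The posterior mean, which is the planned point estimate, is 0.5% at 0/10 and 0.3% at 0/20.

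**Coverage of the nominal 95% placebo interval**, summed over binomial outcomes in both arms. The chance of no deaths in either arm is (1 − p)^(2n).

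| Per arm | True mortality | Chance of no deaths | Coverage |
|---|---|---|---|
| 5 | 10% | 0.9^10 = 35% | 64% |
| 10 | 5% | 0.95^20 = 36% | 64% |
| 10 | 10% | 0.9^20 = 12% | 87% |
| 20 | 10% | 0.9^40 = 1.5% | 94% |

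In the first three rows coverage is within about one percentage point of 1 minus the chance of no deaths (65%, 64% and 88%). The failure is almost entirely the no-death outcome.

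**What does not fail.** With 1/10 v 0/10 the SAP intervals are about 0.2 to 22% (placebo) and 0.1 to 18% (BE1116). With a Jeffreys prior on placebo mortality they are 0.6 to 26% and 0.3 to 20%. With no deaths in either arm, the posterior probability of lower mortality on BE1116 is about 0.52 under the SAP priors, as it should be when the data say nothing.

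**The case against.** The strongest reply has four parts.

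First, the fault needs no deaths in both arms. At the planning rate of 10% coverage is already 94% with 20 per arm and 95% with 30 per arm. This stands. A reader might infer that all small subgroup levels are unreliable under these priors. The calculation does not support that, and the documents do not say how small any level will be.

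Second, a single-arm exact limit is a harsh comparator, because β1 ~ Normal(0, 1²) deliberately lets each arm borrow from the other. This stands in part. Pooling both arms roughly halves the gap, but the SAP limit remains about 3.4 times too low at 10 per arm (16.8/4.9) and 3.5 times at 20 per arm (8.8/2.5).

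Third, no comparison between arms is distorted. A reader might infer that a falsely tight interval for the risk difference would be reported as evidence of no effect. SAP 10.1.2 lists that interval for the primary analysis, but SAP 10.1.4 does not list it for subgroups. The comparative output that it does list stays near 0.52.

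Fourth, the secondary endpoints are less exposed. At the 16% event rate simulated for 24-hour mortality, 10 per arm gives no deaths with probability 0.84^20 = 3%. This stands, so the point reaches SAP 10.2.6 only where a level is equally sparse.

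**Conclusion.** The point holds in a limited form. For a level with no deaths in either arm, the β0 prior is not noninformative, and the listed mortality interval has an upper limit about 6 to 7 times below the exact single-arm limit (30.8/4.9 and 16.8/2.5). Coverage can fall to about 64%. These coverage figures rest on assumed level sizes and on equal mortality in both arms. Only the 10% rate comes from the SAP.

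The consequence is minor. Subgroup results are descriptive, no success criterion uses them, and the gated testing in SAP 10.4 covers only the primary and secondary efficacy endpoints. It would be wrong to infer that the primary analysis is compromised: deaths in the full mITT Population should be numerous enough to swamp the prior.

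**What to change.** Keep the model and the priors. Add a rule to SAP 10.1.4, and to SAP 10.2.6 where a level is equally sparse. It should cover any level with no deaths in either arm or, more broadly, fewer than 5 deaths in an arm. For these levels, show deaths/N with an exact or Jeffreys 95% interval for each arm, in place of or beside the model-based interval. Add a footnote that the model-based interval is driven by the prior.

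Do not repair this by changing the β0 prior alone, for example to Normal(−2.2, 1.5²), which is centred on the 10% planning rate. That ties down only the placebo arm and leaves BE1116 freer to drift towards zero. With no deaths in either arm, the posterior probability of benefit moves from 0.52 to 0.63 (10 per arm), 0.66 (20), 0.68 (30) and 0.70 (50), in favour of BE1116 and without any data. It also under-covers in truly low-risk levels, at about 90% when mortality is 0.5%. Any alternative prior should treat the two arms symmetrically.

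The cost is a sentence in each of two SAP sections and an extra column in the subgroup tables, best settled before database lock. The primary analysis does not change.

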10.2 Analysis of Secondary Efficacy Endpoints

The secondary endpoints (and corresponding summary measures) of the study are listed in [Section 4.1](#).

All secondary efficacy endpoints will be analyzed using the mITT Population. Missing data handling is described in [Section 8.1](#).

10.2.1 Secondary Estimands

Estimands for secondary endpoints are outlined in the following table.

Secondary endpoint	Population	Endpoint	Intercurrent Events	Summary Measure
1	Subjects with traumatic injury and either acute major bleeding (confirmed or suspected) or predicted to receive a large volume blood product transfusion (mITT Population).	All-cause in-hospital mortality up to 24 hours after randomization	Treatment discontinuation – treatment policy strategy Subject receives other medication between randomization and 24 hours – treatment policy strategy	Difference in proportion of subjects who die in-hospital in the BE1116 arm compared with the placebo arm up to 24 hours after randomization
2	Subjects with traumatic injury and either acute major bleeding (confirmed or suspected) or predicted to receive a large volume blood product transfusion (mITT Population).	All-cause in-hospital mortality up to 30 days after randomization	Treatment discontinuation – treatment policy strategy Subject receives other medication after randomization – treatment policy strategy	Difference in proportion of subjects who die in-hospital in the BE1116 arm compared with the placebo arm up to 30 days after randomization

Secondary endpoint	Population	Endpoint	Intercurrent Events	Summary Measure
3	Subjects with traumatic injury and either acute major bleeding (confirmed or suspected) or predicted to receive a large volume blood product transfusion (mITT Population).	Surgical or interventional radiological procedures to stop bleeding related to the primary injury up to 24 hours after randomization	Treatment discontinuation – treatment policy strategy Subject receives other medication between randomization and 24 hours post randomization – treatment policy strategy	Difference in proportion of subjects who receives surgical or interventional radiological procedures to stop hemorrhage

10.2.2 All-cause In-hospital Mortality Within 24 Hours

All-cause in-hospital mortality during primary hospitalization up to 24 hours after randomization will be analyzed and summarized in the same manner as for the primary endpoint. The same noninformative priors as specified for the primary analysis will be used.

10.2.3 All-cause In-hospital Mortality Within 30 Days

All-cause in-hospital mortality up to 30 days after randomization will be analyzed in the same manner as the primary endpoint.

In addition, Kaplan-Meier (KM) plot will be included to display the time to death (see for [Section 8.2.3](#) for derivation) for each treatment group. Discharged and discontinued subjects will be considered censored at the date of discharge/discontinuation. Log-rank p-values will also be provided as an exploratory measure.

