8.5.4 In-hospital Follow-up Period

Subjects will be followed up until death, discharge from hospital, or Day 30, whichever occurs first. If subject is discharged alive prior to 6 hours, then the subject will be followed up to assess 6-hour survival status, SAEs, and AESIs. Transfer to another healthcare facility will be considered as discharge from hospital. For details regarding Informed Consent, refer to [Section 12.3](#) and [Section 12.3.1](#).

The following assessments will be performed:

- IP accountability (to be performed in the IRT system when feasible within 24 hours after randomization)
- Demographics (to be recorded when feasible)*
- Medical history and Charlson Comorbidity Index (to be recorded when feasible)*

- Prior and concomitant medications (medications that impact bleeding and coagulation [including antiplatelets] for at least 1 week prior to randomization; tranexamic acid [if administered]; prohibited concomitant medications administered from trauma time through 6 hours after randomization; and anticoagulants, thrombolytic agents, and procoagulants used to treat AESIs; to be recorded when feasible)*
- Concomitant procedures (any surgical or interventional radiological procedures, or other life-saving interventions, used to treat an SAE or AESI at any time through the study will be recorded)*
- SAEs and AESIs
- Survival status (survival status of the subject during primary hospitalization will be recorded from randomization up to the time of death, hospital discharge, or Day 30, whichever occurs first. The date and time of death / hospital discharge / Day 30 will be recorded, as applicable. For expired subjects, details of their death may be recorded on the Subject Death Record. The survival status check during primary hospitalization will be at 24 hours [the date and time of death / hospital discharge will be recorded, as applicable]. If subject is discharged alive prior to 6 hours, then the subject will be followed up to assess 6-hour survival status, SAEs, and AESIs)*
- Blood product transfusions (eg, RBCs, FFP, whole blood, cryoprecipitate, intraoperative salvaged [cell-saver] blood, and platelets) and IV fluid administrations (crystalloids and / or colloids) before arrival at the hospital through the 24 hours after randomization*
- All surgical or interventional radiological procedures performed to stop bleeding related to the primary injury, through the first 24 hours after randomization*
- Mode of transport to the hospital*

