10.3.2.7 Missing Data

For efficacy endpoints, missing data will be handled according to the following rules.

- All-cause mortality up to 6 hours after randomization: if a subject withdrew from the study prior to 6 hours after randomization, the survival status at the time of study withdrawal will be carried forward to the 6-hour time point.
- All-cause in-hospital mortality up to 24 hours after randomization: if a subject withdrew or discharged from the study prior to 24 hours after randomization, the survival status at the time of study withdrawal or discharged will be carried forward to the 24-hour time point.
- All-cause in-hospital mortality up to 30 days after randomization: if a subject withdrew or discharged from the study prior to 30 days after randomization, the survival status at the time of study withdrawal or discharged will be carried forward to the 30-day time point.
- Use of surgical or interventional radiological procedures to stop bleeding: if a subject withdrew early or died, the usage of any surgical or interventional radiological procedures to stop bleeding up to the time of study withdrawal or death will be carried forward to the 24-hour time point.

Additional missing data will be handled as described in the SAP.

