8.2.3 Survival Status

Survival status at 6 hours, 24 hours and 30 days will be determined as follows:

- All-cause 6-hour mortality:
 - If death is not recorded for the subject, the subject will be considered alive.
 - If death is recorded, the subject will be considered alive at 6 hours if time of death – time of randomization is greater than 6 hours. Otherwise, the subject will be considered dead.
- All-cause in-hospital 24-hour mortality:
 - If available, survival status will be taken directly from the 24 Hours Survival Status eCRF page.
 - Otherwise, the subject will be considered alive if no death was recorded, or if death was recorded but took place more than 24 hours post randomization.
 - If death occurred and took place within 24 hours of randomization, the subject will be considered dead.
- All-cause in-hospital 30-day mortality:
 - If available, survival status will be taken directly from the survival status recorded in the Conclusion of Subject Participation eCRF page.
 - Otherwise, the subject will be considered alive if no death was recorded, or if death was recorded but took place more than 30 days post randomization, considering date and time of death.
 - If death occurred and took place within 30 days of randomization, the subject will be considered dead.

These included cases of withdrawal, discharge and declining to continue participation – if no death was recorded, it will be assumed no death occurred.

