8.2.4 Time to Death

Time from randomization to death will be calculated in hours by subtracting the datetime of randomization from datetime of death.

This calculated time to death will be used only for Kaplan-Meier analysis, not to determine survival status. The same calculation rule applies for time to any censoring events.

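### The 30-day Kaplan-Meier plot censors patients at live discharge, so 1-KM at Day 30 will overstate the in-hospital death proportion analysed in the same section

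*SAP*

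**What the plan says.** The main analysis in SAP 10.2.3 is a proportion: "All-cause in-hospital mortality up to 30 days after randomization will be analyzed in the same manner as the primary endpoint". The matching summary measure in SAP 10.2.1 is "Difference in proportion of subjects who die in-hospital in the BE1116 arm compared with the placebo arm up to 30 days after randomization". Footnotes to the endpoint tables (protocol 2.2.2, SAP Table 1) limit in-hospital mortality to the primary hospitalization. Protocol 8.5.4 adds that "Transfer to another healthcare facility will be considered as discharge from hospital".

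In the proportion, patients who leave hospital alive stay in the denominator as survivors. Protocol 10.3.2.7 says that "the survival status at the time of study withdrawal or discharged will be carried forward to the 30-day time point". SAP 8.2.3 takes the recorded status where there is one and otherwise assumes that no recorded death means no death: "These included cases of withdrawal, discharge and declining to continue participation".

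The Kaplan-Meier plot in SAP 10.2.3 follows a different rule: "Discharged and discontinued subjects will be considered censored at the date of discharge/discontinuation". A log-rank comparison accompanies it: "Log-rank p-values will also be provided as an exploratory measure". For the derivation of time to death the section points to 8.2.3, but the derivation is in 8.2.4, which states: "This calculated time to death will be used only for Kaplan-Meier analysis, not to determine survival status". Neither document plans a competing-risk method for this endpoint or warns the reader about how to read the plot.

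**The concern.** The event in this section is death in hospital during the primary stay. Once a patient has been discharged alive or transferred, that event cannot occur. Kaplan-Meier censoring treats such a patient as still liable to the event, at the same rate as those who remain in hospital. The risk set shrinks with each discharge, so every later death takes a larger step than 1/N. The complement of the curve then no longer estimates the proportion dying in hospital, and the same patients are handled in two incompatible ways within one section.

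Two misreadings could follow. First, a reader who takes 30-day in-hospital mortality from the plot gets a higher figure than the planned proportion. Secondly, if treatment changes time to discharge, the two curves can separate even when deaths are identical. The protocol makes that possibility relevant: section 1.4 lists shorter hospital and ICU stay as a potential benefit, and SAP Table 1 has hospital-free days as an exploratory endpoint. A product that shortened stay without changing deaths would look worse on this plot. The plot is likely to be read for persistence of benefit, since protocol 3.3.1 itself argues persistence from a prior trial's 30-day Kaplan-Meier curves.

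**Working it through.** The plan states no Kaplan-Meier value, 30-day mortality or discharge distribution, so there is no figure of its own to reproduce. The check compares 1-KM at Day 30 with deaths/N.

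**General form.** Take N patients, of whom D1 die before any discharge; c are then discharged alive; D2 of the remainder die in hospital by Day 30.

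- Proportion = (D1 + D2)/N
- 1-KM = 1 - [(N - D1)/N] × [1 - D2/(N - D1 - c)]
- Excess = 1-KM minus proportion = (D2/N) × c/(N - D1 - c)

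The excess cannot be negative. It is zero only if no one is discharged before a late death (c = 0) or no death follows a discharge (D2 = 0).

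**Small example.** 100 patients, 10 deaths on Day 1, 40 discharges on Day 5, 2 deaths on Day 10, 48 still in hospital at Day 30. The proportion is 12.0%; 1-KM = 1 - 0.90 × 48/50 = 13.6%. Without the two late deaths both are 10.0%.

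**Example tied to the SAP.** The 16% rate for 24-hour mortality comes from SAP 16.2.5. The other inputs are assumed: N = 1000 and 20 late deaths. So D1 = 160, there are 840 survivors at 24 hours, and the proportion is 180/1000 = 18.0%.

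| Survivors discharged before the late deaths | Still in hospital, n | 1-KM = 1 - 0.84 × (n - 20)/n | Excess (points) |
|---|---|---|---|
| 25% | 630 | 18.7% | 0.7 |
| 50% | 420 | 20.0% | 2.0 |
| 75% | 210 | 24.0% | 6.0 |

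These rows put all discharges before all late deaths, which is the least favourable ordering for a given discharge fraction.

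**Spread over time (all inputs other than the 16% assumed).** With exponential discharge after Day 1, mean stay 7 to 20 days, and a late death hazard decaying with time constant 3 or 7 days, scaled to 18% or 20% in-hospital deaths, the excess is 0.3 to 4.4 points. A constant late hazard gives 1.9 to 14.1 points. A wider grid (30-day in-hospital mortality 17% to 25%, median stay 5 to 25 days after Day 1, late-death half-time 2 or 5 days) gives 0.1 to 21.4 points. The excess is positive in every scenario.

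**Contrast between arms.**

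- Equal discharge timing: a true 2.0-point difference appears as 1.94 to 2.00 points on the Kaplan-Meier scale.
- Identical deaths, 25% against 50% discharged first (rows 1 and 2 of the table): 20.0 - 18.7 = 1.3 points on Kaplan-Meier, 0 on the proportion.
- Identical deaths (22%), median stays of 10 and 8 days: 1-KM is 26.3% and 28.1%, a spurious gap of 1.9 points before rounding.

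**Log-rank test.** With discharge censored, equal death hazards (constant 0.006 per day after Day 1), 650 per arm and 4000 simulated trials, two-sided rejection was 4.9% with equal stay and 5.0% with mean stays of 10 and 8 days. The test keeps its size as a comparison of cause-specific hazards.

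**Effect of the fix.** In simulated samples of 500 without withdrawals, cumulative incidence with discharge as a competing event (Aalen-Johansen) equalled the proportion to within 2e-16. If 10 withdrawals are censored at 24 hours while discharges stay in the risk set, the tabulated example gives 1 - 0.84 × 810/830 = 18.02% against 18.00%.

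**The case against.** The strongest reply is that no planned number is wrong. SAP 10.2.3 asks for a plot, not a tabulated Day-30 Kaplan-Meier estimate; the proportion, its difference and credible intervals come from the Bayesian logistic model; and the censoring rule is stated openly. SAP 8.2.4 also keeps the time-to-death variable apart from survival status. All of this stands, and it limits the weight of the point. But keeping the derivations apart does not tell a reader that the plot does not show in-hospital mortality.

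A second reply is that the plotted variable is simply time from randomization to death, with discharge as the end of observation, so that censoring is conventional. The wording of 8.2.4 allows that reading. It fits less well with a section whose heading and estimand are in-hospital death. It would also require discharged patients to share the risk of those still in hospital, which is implausible; the direction of bias against 30-day death in or out of hospital is not settled here.

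A third reply is that the sizes reflect chosen inputs. That is correct. Only the 16% comes from the documents, and the 6.0-point row exceeds the decaying-hazard range of 0.3 to 4.4 points.

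**Conclusion.** The concern holds and is minor. As written, the plot will give a Day-30 value of 1-KM above the in-hospital death proportion, on the single condition that at least one in-hospital death follows at least one live discharge. Over 30 days that is practically certain, since protocol 3.3.1 expects later deaths from brain injury, sepsis and organ failure. The size cannot be derived from the documents. It can be a fraction of a point or several points, and it depends mainly on how late the late deaths occur and how early patients leave. The between-arm contrast is nearly unchanged if discharge timing is equal and can be distorted if it is not. The log-rank test does not overstate mortality, and the gated conclusion on 30-day mortality is unaffected. The wrong cross-reference for time to death is a separate clerical error.

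**What to change.** In SAP 10.2.3, replace the Kaplan-Meier plot with a cumulative incidence curve of in-hospital death by arm, with live discharge (including transfer) as a competing event. Equivalently for the Day-30 value, keep discharged patients event-free in the risk set to Day 30. For the curve to end exactly at the analysed proportion, carry withdrawals forward as alive too, as SAP 8.2.3 does; otherwise state that withdrawals are censored and that a small mismatch remains. Either use Gray's test or keep the log-rank test, labelled as a comparison of cause-specific hazards. Correct the time-to-death reference from 8.2.3 to 8.2.4.

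If the sponsor prefers to keep the present plot, a footnote saying that discharge is censored and that 1-KM is not the in-hospital death proportion would prevent the misreading, though the curve itself would stay as it is.

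The full change costs about two sentences in the SAP and one changed censoring or event variable. It needs no new data.
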